5.1.1 Retesting During Screening or Lead-in Period

All screening procedures are to be performed within 4 weeks of the randomization visit except as described below.

Retesting:

A single retest of laboratory parameters and/or other assessments within any single Screening period will be permitted (in addition to any parameters that require a confirmatory value).

Any new result will override the previous result (ie, the most current result prior to Randomization) and is the value by which study inclusion will be assessed, as it represents the subject's most current, clinical state.

Laboratory parameters and/or assessments that are included in [Table 5.1-1](#), Screening Period, may be repeated in an effort to find all possible well-qualified subjects. Consultation with the Medical Monitor may be needed to identify whether repeat testing of any particular parameter is clinically relevant.

Extended Screening:

Subjects that experience an acute infection or initiate treatment for latent TB may extend the screening period to 56 days, as long as the infection did not require hospitalization or administration of parenteral antibiotics agents. Under these circumstances, all screening procedures except IVRS enrollment, height/weight, chest x-ray, TB testing, HepB/C, HIV, quantitative immunoglobulins, and anti-SSA should be repeated prior to randomization.

Rescreening:

Subjects that are screen failures may be considered for re-screening if the investigator feels a change in status may render the subject eligible. Laboratory parameters and/or assessments that are included in [Table 5.1-1](#), Screening Procedural Outline, should be repeated in an effort to find all possible well-qualified subjects. Consultation with the Medical Monitor may be needed to identify whether repeat testing of any particular parameter is clinically relevant. The subject will need to sign a new informed consent and be reenrolled with a new subject number via the IVRS. Some tests such as chest x-ray, may not need to be repeated if they were performed within the protocol defined window.

5.1.2 Order of Study Assessments

It is strongly encouraged that study assessments be performed in the following order:

- 1) Patient reported outcomes (PROs) questionnaires
- 2) Salivary Flow
 - a) Unstimulated salivary flow
 - b) Stimulated salivary flow
- 3) Ophthalmologic Assessments - there is a ± 5 day window for the completion of these assessments
 - a) Schirmer test

- b) Tear break-up time
- c) Ocular staining
- 4) AE collection
- 5) Vital signs
- 6) Joint assessments
- 7) Investigator assessments
- 8) Blood draws
- 9) Study Drug Administration

5.1.3 Study Drug Administration Window

Self-administration must be observed for compliance and technique at office visits.

Administration Windows

SC injections of study medication may be administered ± 3 days around the target day. Subjects who miss the dose window should skip the SC injection and wait until the next targeted administration day.

If abnormal laboratory test results or clinical assessment indicate an adverse event that, in the judgment of the investigator, could place the subjects at risk with continued administration of study medication, study medication administration should be skipped. Subjects may receive further study medication only if resolution of the AE or abnormal laboratory finding is documented or, at a minimum, the subject's status returns to what it was at baseline.

5.2 Study Materials

The following materials will be provided for use during the trial:

- Diary cards to record SC dosing administration
- Written instructions on how to use the SC syringes
- eCRF instructions
- Pregnancy Surveillance Forms
- Subject and Investigator-rated questionnaires/scales (paper)
- Ruler, 10 cm for measurement of Visual Analog Scales
- Drug Inventory binder (optional)
- Interactive Voice Response System (IVRS) worksheets
- Laboratory test kits for all required laboratory testing
- Cooler bags and gel packs will be provided to assist subjects in transporting study drug
- Sharps containers will be provided to assist subjects in disposing of used SC syringes
- Tote bags to transport cooler bags, sharp containers and study drug

5.3 Safety Assessments

On Day 1, the results of all assessments must be reviewed to ensure that eligibility requirements are met before contacting the Central Randomization System for the subject's randomization assignment.

Subjects who terminate treatment early should complete the appropriate Early Termination Visit and the Post Drug Follow-up Visits. The Early Termination Visit should be as soon as possible after the last dose of study medication.

All assessments should be performed or administered prior to study drug administration unless otherwise indicated.

Only data for the procedures and assessments specified in this protocol should be submitted to BMS on a case report form. Additional procedures and assessments may be performed as part of standard of care; however, data for these assessments should remain in the subject's medical record and should not be provided to BMS, unless specifically requested from BMS.

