4.9 Retained Samples for Bioavailability / Bioequivalence

Not Applicable.

Table 5.1-1: Screening Procedural Outline (IM101603)

Procedure	Screening Visit ^a	Screening Visit 2 ^b	Notes
Urinalysis	X		
HBsAg, anti-HBcAb (anti-HBsAb where required)	X		If positive, obtain HBV DNA (see Section 5.3.7.5)
Hepatitis C Antibody	X		If positive, reflex to HCV confirmation such as PCR
HIV	X		Testing performed locally, if required
Anti-Ro Antibody (anti-SSA)	X		
Quantitative Immunoglobulins (IgG, IgA, IgM)	X		
Urine/Serum Pregnancy Test	X	X	WOCBP only, see Appendix 1 for details
Disease Assessments			
ESSDAI	X	X	
Stimulated Salivary Flow	X	X	See Section 5.4.2

^a The duration of the screening period should not exceed 28 days.

^b Subjects that experience an acute infection or initiate treatment for latent TB may extend the screening period to 56 days. Under these circumstances, all screening procedures except subject consenting, IVRS enrollment, height/weight, immunoglobulins, urinalysis, chest x-ray, TB testing, HepB/C and HIV should be repeated prior to randomization.

Table 5.1-2: Double-Blind Treatment Period - Procedural Outline (IM101603)^{a,b}

Procedure	Day 1	Day 29 (Wk 4)	Day 57 (Wk 8)	Day 85 (Wk 12)	Day 113 (Wk 16)	Day 141 (Wk 20)	Day 169 (Wk 24)/ Early Term.	Notes
Quantitative Immunoglobulins (IgG, IgM, IgA)	X	X		X	X		X	
hsCRP	X	X	X	X	X	X	X	
ESR	X	X	X	X	X	X	X	Performed locally, kits provided centrally.
Rheumatoid Factor, IgM-RF	X	X		X	X		X	
β-2-Microglobulin (B2M)	X	X		X	X		X	
Free Light Chain (FLC)	X	X		X	X		X	
Complement (C3, C4, CH50)	X	X		X	X		X	
Anti-Ro Antibody (anti-SSA)	X	X		X	X		X	
Anti-La Antibody (anti-SSB)	X	X		X	X		X	
Anti-centromere Antibody (ACA)	X	X		X	X		X	
Anti-CCP2	X	X		X	X		X	
	L			L			L	
	L						L	
	L			L			L	
	L							
	L						L	
	L			L			L	

Table 5.1-2: Double-Blind Treatment Period - Procedural Outline (IM101603)^{a,b}

Procedure	Day 1	Day 29 (Wk 4)	Day 57 (Wk 8)	Day 85 (Wk 12)	Day 113 (Wk 16)	Day 141 (Wk 20)	Day 169 (Wk 24)/ Early Term.	Notes
Pharmacokinetic (PK) Assessments								
Pharmacokinetic (PK) Sampling	X	X	X	X	X	X	X	Samples collected predose, except for ET. See additional PK sampling for PK sub-study (Table 5.1-5). See more details in Section 5.5.1 .

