^b All subjects who discontinue study drug during the double-blind period should continue to comply with protocol specified procedures as outlined in [Table 5.1-2](#). The only exception to this requirement is when a subject withdraws consent for all study procedures including post-treatment study follow-up or loses the ability to consent freely (i.e., is imprisoned or involuntarily incarcerated for the treatment of either a psychiatric or physical illness).

^c Procedure to be performed by an ophthalmologist or optometrist experienced in the diagnosis and treatment of Sjögren’s syndrome patients. Eye assessments must be performed within ± 5 days of the study visit. See [Section 5.4.3](#) for additional detail.

Table 5.1-3: Open-Label Treatment Period Procedural Outline (IM101603)^a

Procedure	Day 169 (WK 24) ^b	Day 197 (Wk 28)	Day 225 (Wk 32)	Day 253 (Wk 36)	Day 281 (Wk 40)	Day 309 (Wk 44)	Day 337 (Wk 48)	Day 365 (Wk 52)/ End of Treatment	Notes
ESR		X	X	X	X	X	X	X	Performed locally, kits provided centrally.
Rheumatoid Factor; IgM-RF				X				X	
Free Light Chain (FLC)				X				X	
β-2-Microglobulin (B2M)				X				X	
Complement (C3, C4, CH50)				X				X	
Anti-Ro Antibody (anti-SSA)				X				X	
Anti-La Antibody (anti-SSB)				X				X	
Anti-centromere Antibody (ACA)				X				X	
Anti-CCP2				X				X	
Pharmacokinetic (PK) Assessments									
Pharmacokinetic (PK) Sampling								X	No sample collection at EOT.
Immunogenicity (anti-abatacept antibody) testing								X	No sample collection at EOT.
Biomarker Assessments									
Serum Biomarkers				X				X	See Section 5.6.3
Saliva Biomarkers				X				X	See Section 5.6.4
Blood Immunophenotyping								X	See Section 5.6.5
PBMCs				X				X	See Section 5.6.5

Table 5.1-3: Open-Label Treatment Period Procedural Outline (IM101603)^a

Procedure	Day 169 (WK 24) ^b	Day 197 (Wk 28)	Day 225 (Wk 32)	Day 253 (Wk 36)	Day 281 (Wk 40)	Day 309 (Wk 44)	Day 337 (Wk 48)	Day 365 (Wk 52)/ End of Treatment	Notes
Efficacy Assessments									
ESSDAI		X	X	X	X	X	X	X	
Tender (68)/Swollen (66) Joint Count		X	X	X	X	X	X	X	
Physician's Global Assessment of Disease Activity		X	X	X	X	X	X	X	
ESSPRI		X	X	X	X	X	X	X	
PROMIS Fatigue		X	X	X	X	X	X	X	
Subject's Global Assessment of Disease Activity		X	X	X	X	X	X	X	
Mouth (Oral) dryness (NRS)		X	X	X	X	X	X	X	
Eye (Ocular) dryness (NRS)		X	X	X	X	X	X	X	
SF-36				X				X	
Female Sexual Function Index (FSFI)				X				X	
Unstimulated Salivary Flow				X				X	
Stimulated Salivary Flow				X				X	

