5.4.3 Ophthalmologic Assessments

The following procedures should be performed at baseline/Day 1, and Days 85, 169, 253, 365 and early termination by an ophthalmologist trained in the ophthalmologic assessment of patients with Sjögren's Syndrome. Assessments may also be performed by an optometrist who is familiar with the required testing and experienced in diagnosing and treating patients with dry eyes associated with Sjögren's syndrome. A visit window of 5 days relative to the study visit to perform the ophthalmologic assessments is acceptable, but all ophthalmologic assessments must be performed during the same visit. Subjects should be instructed to not use parasympathomimetic agents, such as pilocarpine and cevimeline for the 48 hours prior to ocular assessments. Subjects should not use cyclosporine, lifitegrast, or corticosteroid eye drops or artificial tears for 12 hours prior to the assessment. Ophthalmologic assessments performed on days 85, 169, 253, 365 and early termination should be performed at approximately the same time of day as the baseline assessment.

- Schirmer's test: The test (without anesthesia) is performed by placing a narrow calibrated filter-paper strip in the inferior cul-de-sac of each eye. Aqueous tear production is measured by the length in millimeters that the strip wets during the 5 minute test period.
- Tear break-up time (TBUT): Determined by instilling fluorescein dye and evaluating the stability of the pre-corneal tear film. After several blinks, the tear film is examined using a broad beam of the slit-lamp (biomicroscope) with a cobalt blue filter. The TBUT, defined as the time in seconds between the subject's last blink and the first appearance of a random dry spot on the corneal surface, is measured 3 times and the mean value is recorded.
- Ocular surface staining: The test is performed by instillation of fluorescein dye and lissamine green dye to stain the cornea and conjunctiva, respectively. After instilling the dye, the ocular surface is examined through a slit lamp (biomicroscope) and the staining pattern is recorded per the method described in Whitcher, et al. (Rose Bengal stain as a substitute for lissamine green is acceptable only in regions in which lissamine green is not available.)

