7.3.2 Demography and Baseline Characteristics

Demographic and baseline disease characteristics will be summarized by randomized treatment group and overall based on the modified ITT analysis population. For continuous variables, they will be summarized using means, standard deviations, median, Q1, Q3 and ranges (minimum and maximum), based on non-missing observations. The distribution of categorical variables will be summarized by treatment group using frequency and percentage. For categorical variables, percentages will be calculated out of the total number of subjects in the modified ITT population, overall and by treatment group (i.e., each denominator includes the number of subjects with missing/unknown values for the characteristic and missing is included as a category).

Table 7.3.2-1: Demographic and Baseline Characteristics

Characteristic	Summarized as	Categories
Age (years)	Categorical and Continuous	< 65 yrs., ≥ 65 yrs. ≤ 50 yrs., > 50 yrs.
Gender	Categorical	Male Female

Table 7.3.2-1: Demographic and Baseline Characteristics

Characteristic	Summarized as	Categories
Race	Categorical	White Black or African American Asian Other
Ethnicity (to be summarized only for USA subjects)	Categorical	Hispanic/Latino Non Hispanic/Latino
Region	Categorical	North America South America Europe Asia ROW (see APPENDIX 3)
Body Weight (kg)	Continuous and Categorical	< 60kg 60 - 100kg > 100kg
Randomization stratification factors as recorded on IWRS	Categorical	Baseline Hydroxychloroquine use (YES/NO) Baseline oral corticosteroid use (YES/NO) Screening and Baseline Stimulated Salivary Flow (< 0.1mL/min, ≥ 0.1mL/min) Japan (YES/NO) and all possible combinations of these 4 stratification factors
Randomization stratification factors as recorded on CRF	Categorical	Baseline Hydroxychloroquine use (YES/NO) Baseline oral corticosteroid use (YES/NO) Screening and Baseline Stimulated Salivary Flow (< 0.1mL/min, ≥ 0.1mL/min) Japan (YES/NO) and all possible combinations of these 4 stratification factors on CRF
2016 ACR-EULAR Classification Criteria met:	Categorical	Yes/No

 • Labial salivary gland with focal lymphocytic sialadenitis and focus score ≥ 1 • Anti-SSA (Ro)+ • Ocular Staining score ≥ 5 (or van Bijsterveld score ≥ 4) on at least one eye • Schirmer ≤ 5mm/5min on at least one eye • Unstimulated whole saliva flow rate ≤ 0.1ml/min 		
ESSDAI Total Score	Continuous	

Table 7.3.2-1: Demographic and Baseline Characteristics

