8.2 Baseline Measures

For each subject, the baseline value of a parameter is defined as the last assessment of that parameter on or prior to the date/time of the first dose of the double-blind study medication.

If time of measurement of a parameter or time of first dose are missing, then the baseline value is defined as the last assessment of that parameter on or prior to the date of the first dose of the double-blind study medication.

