APPENDIX 2 RELEVANT PROTOCOL DEVIATIONS

- Eligibility Deviations:
 - Subjects who did not meet 2016 ACR/EULAR classification criteria at screening
 - Subjects with ESSDAI < 5 at screening
 - Subjects who were anti-SSA/Ro negative at screening
 - Subjects who have received IV, IM, SC or intra-articular corticosteroids within 4 weeks of first double-blind abatacept dose
 - Subjects who have taken MTX within 12 weeks of first double-blind abatacept dose
 - For subjects on hydroxychloroquine at first date of double-blind abatacept dose: subjects on hydroxychloroquine for < 12 weeks and/or the dose not stable for at least 4 weeks prior to Day 1
- Incorrect dosing:
 - Subjects received treatment different than randomized group
 - If more than 4 consecutive doses are missed just prior to the primary time point, Day 169
- Restricted and Prohibited medications:
 - Subjects receiving a single IM, IV, SC or oral course of high dose of corticosteroid (> 10mg/day for > 1 consecutive days) in the Double-Blind Treatment Period within 56 days of primary time point (i.e. the efficacy assessment done at Day 169).
 - Subjects receiving a non-biologic DMARD (except hydroxychloroquine already taken at Day 1) at any time during the Double-Blind Treatment Period up to the day prior to the efficacy assessment done at Day 169
 - Subjects receiving a biologic DMARD at any time during the Double-Blind Treatment Period up to the day prior to the efficacy assessment done at Day 169
 - Subjects adding hydroxychloroquine during the Double-Blind Treatment Period up to the day prior to the efficacy assessment done at Day 169 while not on this medication at Day 1.

Note: Day 169 is the time point used for the **primary analysis** of ESSDAI at Day 169.

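### The Day 1 eye-exam window extends past the first dose, conflicts with the pre-dose rules, and can leave a subject with no baseline for three secondary endpoints

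*Protocol*

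**What the plan says.** **When the eye tests are done.** Protocol 5.4.3: "The following procedures should be performed at baseline/Day 1, and Days 85, 169, 253, 365 and early termination by an ophthalmologist". Screening is not in that list. The disease assessments visible in the screening schedule (Table 5.1-1) are ESSDAI and stimulated salivary flow only.

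**The window.** It appears in three places, none of which treats Day 1 differently:
- Table 5.1-2, footnote c: "Eye assessments must be performed within ± 5 days of the study visit".
- Section 5.1.2 gives ±5 days, beside the eye tests in the order-of-assessments list.
- Section 5.4.3 gives no direction: "A visit window of 5 days relative to the study visit to perform the ophthalmologic assessments is acceptable".

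**The pre-dose rules.** Protocol 5.3: "On Day 1, the results of all assessments must be reviewed to ensure that eligibility requirements are met before contacting the Central Randomization System". Section 5.3 also puts assessments ahead of study drug, except where the protocol indicates otherwise. Sections 3.1.2 and 4.5 place the injection after all assessments on office-visit days.

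**The SAP.** Baseline is "the last assessment of that parameter on or prior to the date/time of the first dose of the double-blind study medication" (8.2). In Table 8.5-1 the Day 1 window for eye tests ends on Day 1, and Days 2 to 127 belong to the Day 85 visit. SAP 7.5.2.1 chooses the study eye from baseline ocular staining, then baseline Schirmer, then tear break-up time.

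**The concern.** A symmetric window suits follow-up visits, but the baseline visit has a hard stop at the first injection. A site that books the ophthalmologist a few days after Day 1 can point to footnote c and consider itself compliant, while the SAP will not accept the result as baseline. The loss cannot be repaired, because an untreated value cannot be obtained once the subject has been dosed. One late appointment affects three endpoints together, since 5.4.3 requires all the eye tests to be done at the same visit.

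**Working it through.** The plan states no figure on this point, so the check compares the rules and counts days.

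**Day 1**
1. The window is ±5 days around Day 1 (Table 5.1-2 footnote c; 5.1.2). Its last day is 1 + 5 = Day 6, so Days 2 to 6 lie inside it.
2. The first dose is on Day 1, so an exam on Days 2 to 6 follows it. SAP 8.2 therefore does not accept that exam as baseline.
3. Table 8.5-1 assigns the same exam to Day 85 (Days 2 to 127). SAP 8.5 keeps the value nearest the target day. An exam on Day 6 is 85 − 6 = 79 days from target, so a regular Day 85 exam replaces it.
4. SAP 8.2 offers no fallback to a post-dose value, and no earlier eye exam appears in 5.4.3 or in the visible part of Table 5.1-1. The baseline is missing.
5. Change from baseline (SAP 7.1.1) then cannot be computed at any visit. The repeated-measures model in SAP 7.5.2.1 also needs the baseline value as a covariate. The study eye and non-study eye are undefined, and the two-eye average has no baseline either. The subject drops out of all three endpoints.

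**Whether the window or the pre-dose rules prevail**

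| Text | Effect on a Day 2–6 exam |
|---|---|
| Table 5.1-2 footnote c; 5.1.2 | Within window |
| 5.4.3 | Within window if read as two-sided |
| 5.3, review before randomisation | Barred, if the eye results are among those to be reviewed |
| 5.3, assessments before drug | Barred, unless the eye window counts as the exception that the sentence allows |
| 3.1.2 and 4.5 | Barred, if an eye visit on another date is covered by a rule about office-visit days |
| 5.1.2, order list | Eye tests third and drug ninth, but the order is only strongly encouraged |

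No sentence settles the matter. By contrast, 5.9 gives the baseline biopsy a window that runs only before the start of dosing, so the protocol does write a one-sided window elsewhere.

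**Day 169**
The same window runs to 169 + 5 = Day 174. Open-label dosing starts on Day 169 (Protocol 3.1.3). Note a to SAP Table 8.5-1 closes the double-blind window at the first open-label dose if that comes before the post-dose limit. For a subject dosed open-label on Day 169, an eye exam on Days 170 to 174 meets the protocol window but is not a Day 169 value in the SAP.

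**The case against.** The strongest reply is that the protocol already forbids a late Day 1 exam. Sections 3.1.2, 4.5 and 5.3 all point to assessment before dosing, and the ±5 days is a general window written for every eye visit. No sentence says that a Day 1 eye exam may follow the first dose. This is largely right: a reader might infer that the plan plainly permits a post-dose baseline, and the documents do not support that. What remains is a conflict, because each pre-dose rule has a limit or an exception that a specific eye window could be read to meet.

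A reader might also infer that subjects can be randomised before eligibility is established. SAP Table 7.3.2-1 lists eye items among the classification criteria (for example "Schirmer ≤ 5mm/5min on at least one eye"), and SAP Appendix 2 counts as deviations "Subjects who did not meet 2016 ACR/EULAR classification criteria at screening". The documents supplied do not support that step. Appendix 3 and part of Table 5.1-1 are not available, so it is unknown whether a subject needs an eye item to qualify or whether earlier results may be used. Protocol 3.3.1 has prior biopsy reports collected, which suggests that existing evidence can count. A late Day 1 exam also does not by itself mean that the criteria were unmet at screening.

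Nor is a baseline missing at randomisation the harm. An exam after randomisation but before the first dose is a valid baseline under SAP 8.2.

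Finally, the SAP refers to later amendments that updated study assessments, and that protocol text was not supplied. The window may since have been changed.

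**Conclusion.** The point holds as an unreconciled conflict with a real but limited consequence. An exam on Days 2 to 6 satisfies the eye window, yet under the SAP it leaves the subject without a baseline for Schirmer's test, ocular staining and tear break-up time.

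The documents give no rate of late exams, so the number of subjects lost cannot be calculated. It is zero if every site follows the pre-dose rules, and no upper figure can be supported. The three endpoints are non-key secondary, outside the hierarchical test and without p-values (SAP 7.5). Power and type I error for the primary and key secondary endpoints are untouched.

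The conclusion assumes that no screening eye exam is listed in the missing rows of Table 5.1-1 and that later amendments left the window unchanged. The change is worth making because it is cheap and a lost baseline cannot be recovered.

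**What to change.** - In Protocol 5.4.3, 5.1.2 and footnote c of Table 5.1-2, make the Day 1 eye window one-sided: Day −5 to Day 1, completed before the first dose. The ±5 days can stay at Day 85.
- Reconcile the later side of the Day 169 eye window with note a to SAP Table 8.5-1, so that an exam allowed by the protocol also counts as a Day 169 value.

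The cost is a short wording change in three places and one clarification at Day 169. No extra exam is needed. The only practical downside is slightly tighter ophthalmology scheduling.
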